3. OBJECTIVES AND ENDPOINTS

3.1. Objectives and Endpo	ints
Primary Objective	Primary Endpoint
To assess the effect of mitigation treatments on bruising in the buttocks of subjects with cellulite after the first treatment of QWO (CCH- aaes).	• The proportion of subjects by buttock at each level of bruising on the Investigator Assessment of Bruising Severity Scale, at Day 4, 3 days after QWO (CCH-aaes) injection. This 5-level scale ranges from 0 to 4, with 0 indicating no bruising or almost none, and 4 indicating very severe bruising.
Secondary Objectives	Secondary Endpoints
To assess investigator assessment of bruising with mitigation treatments in subjects with cellulite after the first treatment of QWO (CCH-aaes)	 The proportion of subjects for whom the investigator reported an improvement of bruising on the mitigation treated buttock on Days 4 and 7 as measured on the Investigator-Bruising Improvement Scale (I-BIS), a 3-point Likert scale, with a score on the higher end of the range indicating improvement with treatment. The proportion of subjects by buttock with bruising at each level of the Investigator Assessment of Bruising Severity Scale, by visit. This 5-level scale ranges from 0 to 4, with 0 indicating no bruising or almost none, and 4 indicating very severe bruising.
To assess subject assessment of bruising with mitigation treatments in subjects with cellulite after the first treatment of QWO (CCH-aaes).	 The proportion of subjects treated with QWO (CCH-aaes) reporting an improvement of bruising on the mitigation treated buttock on Days 4 and 7 as measured on the Subject-Bruising Improvement Scale (S-BIS), a 3-point Likert scale, with a score on the higher end of the range indicating improvement of bruising with treatment. The proportion of subjects by buttock bothered by the appearance of bruising on each of their buttocks on the Patient Bother by Bruising Scale, a 4-point scale, with a score of 1 indicating not bothered.
To assess the effect of mitigation treatments on bruising in the buttocks of subjects with cellulite after the first treatment of QWO (CCH- aaes).	• The proportion of subjects by buttock with bruising at each level of the Investigator Assessment of Bruising Severity Scale, by visit. This 5-level scale ranges from 0 to 4, with 0 indicating no bruising or almost none, and 4 indicating very severe bruising.

3.1. Objectives and Endpoints

Secondary Objectives	Secondary Endpoints
To assess the level of aesthetic improvement of cellulite after treatment of QWO (CCH-aaes) with and/or without bruising mitigation treatment.	• The proportion of subjects with an improved (+1 or better) score on the Investigator-Global Aesthetic Improvement Scale (I-GAIS) for either buttock at the Day 71 Visit compared to Baseline. The I-GAIS is a 7-level scale ranging from +3 (very much improved) to -3 (very much worse).
To assess the safety of QWO (CCH-aaes) with mitigation treatment in subjects with cellulite.	• Percentage of subjects reporting each adverse event (AE) and treatment emergent adverse event (TEAEs).
Exploratory Objective	Exploratory Endpoint

4. STUDY DESIGN

4.1. Overall Design

This is a Phase 4, multicenter, open-label, multiple dose study to assess the effect of mitigation treatments on injection site bruising and safety in adult women with moderate cellulite in the buttocks treated with QWO (CCH-aaes). Approximately 75 subjects will be screened in order to enroll approximately 48 subjects in 6 cohorts.

At the Screening Visit, subjects who meet all inclusion criteria and have no exclusion criteria according to the investigator's assessment will be assigned to 1 of 6 treatment cohorts. Subjects will be allocated to cohorts using a site specific Mitigation Treatment Assignment Table provided by the sponsor.

Pending site capabilities and available mitigation treatments, each site will administer each mitigation treatment, with approximately 1-3 subjects assigned to each mitigation treatment as shown in Table 1. Mitigation treatments will be administered at or after the initial treatment session of QWO (CCH-aaes).

		QWO (CCH-aaes) ^a		Mitigation Treatment	
	Ν	Left Buttock	Right Buttock	Left Buttock	Right Buttock
Cohort 1	8	Up to 0.84 mg	Up to 0.84 mg	None	
Cohort 2	8	Up to 0.84 mg	Up to 0.84 mg	Compressi	on garment
Cohort 3	8	Up to 0.84 mg	Up to 0.84 mg	None	Instant cold packs
Cohort 4	8	Up to 0.84 mg	Up to 0.84 mg	None	Arnica patches
Cohort 5	8	Up to 0.84 mg	Up to 0.84 mg	None	INhance Post- Injection Serum with TriHex Technology
Cohort 6	8	Up to 0.84 mg	Up to 0.84 mg	None	PDL treatment ^b

Table 1: Distribution of Mitigation Treatments

^a For each subject, an identical dose and injection count of QWO (CCH-aaes) should be administered for the first treatment session to each buttock. The number of injections may differ among subjects. ^bPulse dye laser (PDL) may be used at the settings selected according to the investigator's discretion.

Eligible subjects will receive up to 0.84 mg of QWO (CCH-aaes) per buttock in both buttocks for a total dose of 1.68 mg per treatment session for 3 treatment sessions (Day 1, Day 21 ± 3 days, and Day 43 ± 3 days). To reduce variance in the bruising observed on the left and right buttock of a subject after the first treatment session of QWO (CCH-aaes), each buttock should be treated with the same number of QWO (CCH-aaes) injections on Day 1, of up to 12 injections per buttock. The number of injections may differ between treatment sessions; 12 injections per buttock during the second and third treatment sessions. The number of injections per buttock per subject may differ among subjects.

Subjects will return to the site approximately on Days 2, 4, 7, and 14 (ie, 1, 3, 6, and 13 days after injection on Day 1) for additional evaluations and digital photography obtained with standardized parameters. After the first mitigation treatment session, on Days 4 and 7, the effect of mitigation treatments on the severity of bruising will be assessed using the I-BIS and the Investigator Assessment of Bruising Severity Scale. The effect of mitigation treatments on the severity of bruising will be assessed by subjects on the S-BIS and the Patient Bother by Bruising

Scale. Safety will be assessed by collecting AEs, and TEAEs and assessing injection site reactions in the buttocks throughout the study.

At the investigator's discretion, for the second and third QWO (CCH-aaes) treatment sessions on Days 22 and 43, subjects will be permitted to receive the same mitigation treatment to the right buttock as received during the first QWO (CCH-aaes) treatment session. The severity of bruising will be assessed at each visit. Subject and investigator assessments of satisfaction, aesthetic improvement, and digital photography will also be conducted on Days 22 (\pm 3 days) and 43 (\pm 3 days). Subjects will return to the site for last study visit on Day 71 for additional investigator assessments of bruising and digital photography.

Subjects will participate in the study for approximately 92 days.

4.2. Scientific Rationale for the Study Design

The most common AE in previous studies of QWO (CCH-aaes) was injection site bruising (QWO Prescribing Information). Ecchymosis that occurs after an injury is generally referred to as a bruise (Verner et al, 2019). Bruising after the first treatment of QWO (CCH-aaes) is the most robust (ie, greater frequency, greater severity, longest duration) as compared to the bruising after the second or third treatments (CSR EN3835-205). Bruising typically resolves within 21 days.

The photographic substudy of Study EN3835-205, depicted bruising over time in photocollages, Investigators that participated in the investigational studies of QWO (CCH-aaes), and/or aesthetic medicine specialists who have viewed these photocollages have expressed interest in evaluating the effects of mitigation treatments to reduce QWO (CCH-aaes)-induced bruising. Mitigation treatments supported by the literature or commonly used to reduce bruising either post-injection or procedures in clinical practice have been selected for evaluation in this study.

To ensure a balanced approach in the assessment of bruising among the sites and investigators, a Mitigation Treatment Assignment Table will be used to assign 1-3 subjects per mitigation treatment per site (pending site capabilities, eligible subjects, and available mitigation equipment).

Subjects with Fitzpatrick skin types of I-III are included in this study. This aligns with the approach taken by Widegrow et al (2020) in another study conducted evaluating mitigation treatments on bruising.

The endpoints evaluating the effect of the mitigation treatments on bruising will be limited to the time period after the first injection of QWO (CCH-aaes) when characterization of bruising of the unmitigated buttock is more robust (greater frequency, more severe, and longest duration) than after the second and third injections of QWO (CCH-aaes). This will limit confounding introduced by the decreased bruising observed over subsequent treatments of QWO (CCH-aaes) when interpreting the effects of the mitigation treatments.

At the investigator's discretion, for the second and third QWO (CCH-aaes) treatment sessions, subjects are permitted to use the same mitigation treatment in the same buttock (as applicable) that received mitigation treatment for the first QWO (CCH-aaes) treatment session.

4.2.1. Changes to the Study Design Due to COVID-19

The COVID-19 public health emergency has disrupted the conduct of clinical research throughout the world. At Endo Pharmaceuticals Inc. (Endo), ensuring the safety of clinical study subjects is our primary concern. In addition, the integrity of data obtained from clinical studies must be ensured.

To ensure subject safety and protect data integrity Endo will allow remote visits for certain study and safety assessments. This is aligned with the *FDA Guidance on Conduct of Clinical Trials of Medical Products during COVID-19 Public Health Emergency* (March 2020, updated 21 September 2020),

Additionally, subjects impacted by the health emergency will be allowed to continue in the study and complete assessments when the investigational sites re-open as follows:

• If a subject had received any dose of QWO (CCH-aaes) in the study prior to an interruption will be allowed to continue in the study.

4.3. Justification for Endpoints

The primary endpoint will be the investigator's assessment of bruising based on observed, inperson assessments during the first treatment session. The subject will not be able to directly view the bruised skin (ie, would have to use reflection in the mirror) and lighting may not be standardized. As such subject viewing of the bruise might be less authentic than direct viewing by the investigator.

The effect of mitigation treatments that are bilaterally administered (eg, compression garments) will be evaluated by the investigator by comparing bruising on each buttock (both of which receive mitigation treatment) vs bruising observed in the control arm (Cohort 1) that is not receiving mitigation treatment. Subjects in this group will not be able to compare their bruising to bruising on buttocks with no mitigation.

The effect of unilaterally applied (right buttock only) topical mitigation treatments (ie, arnica patches, INhance, PDL treatment) will be assessed by comparing the bruising in the mitigation-treated buttock to the contralateral buttock that did not receive mitigation treatment. As such, in unilateral mitigation treatment cohorts, subjects will serve as their own control.

4.4. Justification for Dose

The doses of the mitigation treatments selected are based on the published literature and the experience of the collaborative investigators.

During this study, both buttocks will be treated with QWO (CCH-aaes) at the doses described in the QWO Prescribing Information. Subjects can receive up to 12 injections of QWO (CCH-aaes) to each buttock. For the first treatment session, the number of injections and dose of QWO (CCH-aaes) administered to each buttock should be identical.

4.5. End of Study Definition

A subject is considered to have completed the study if the subject has completed the Day 71 visit. The end of the study is defined as the completion of the final assessment for the last subject enrolled in the study.

5. SELECTION AND WITHDRAWAL OF SUBJECTS

5.1. Subject Inclusion Criteria

In order to be eligible to participate in the study, on Screening and/or Day 1, subjects must:

- 1. Voluntarily sign and date an informed consent agreement.
- 2. Be a female between ≥ 18 years of age and ≤ 50 years old.
- 3. Have both buttocks with:
 - a. a CR-PCSS score of 3 (moderate) as reported by the Investigator, and
 - b. a Hexsel CSS Subsection D "Grade of laxity, flaccidity, or sagging skin" score of 0 (absence of laxity, flaccidity, or sagging skin) or 1 (slightly draped appearance).
- 4. Have a body mass index between ≥18 and ≤30 kg/m², and intends to maintain stable body weight throughout the duration of the study (a variation of ≤10% from baseline body weight is permitted).
- 5. Have a Fitzpatrick skin rating of I-III.
- 6. Be willing to apply sunscreen before each exposure to the sun while participating in the study (ie, Baseline through end of study).
- 7. Be judged to be in good health, based upon the investigator's medical judgement and the results of a medical history and physical examination at Screening.
- 8. Be willing and able to cooperate with the requirements of the study.
- 9. Have ability to read, complete and understand the patient-reported outcomes rating instruments in English.

5.2. Subject Exclusion Criteria

A subject will be excluded from study participation if the subject:

- 1. Has any of the following systemic conditions:
 - a. Coagulation disorder including but not limited to a Factor II, V, VII, or X deficiency.
 - b. Skin pigmentation disorder.
 - c. Evidence or history of malignancy (other than excised basal-cell carcinoma) unless there has been no recurrence in at least 5 years.
 - d. History of keloidal scarring or abnormal wound healing.
 - e. Concurrent diseases or conditions that might interfere with the conduct of the study, confound the interpretation of the study results, or endanger the subject's well-being including but not limited to rheumatoid arthritis and/or other rheumatoid disease(s), Vitamin K deficiency, or liver diseases. Any questions about concurrent diseases should be discussed with the Medical Monitor.
 - f. Evidence of clinically significant abnormalities on physical examination or vital signs.
- 2. Has any of the following local conditions in the buttocks:
 - a. History of lower extremity thrombosis or post-thrombosis syndrome.
 - b. Vascular disorder (eg, varicose veins, telangiectasia, vasculitis) in area to be treated.

- c. Inflammation or active infection in the buttocks.
- d. Active cutaneous alteration including rash, eczema, or psoriasis.
- e. Has a tattoo in the buttocks, visible in clinical photographs.
- 3. Has skin laxity or linear undulations on either buttock that can be effaced by lifting skin.
- 4. Requires the following concomitant medications during the study and cannot discontinue these medications within the time specified before QWO (CCH-aaes) treatment.
 - a. Antiplatelet medication (clopidogrel [Plavix[®]] including aspirin at any dose within 14 days of treatment.
 - b. Anticoagulants, such as warfarin (Coumadin[®]); heparin analogues within 14 days of treatment.
 - c. Non-steroidal anti-inflammatory drugs (NSAIDS), such as ibuprofen (Motrin[®], Advil[®]) and naproxen (Aleve[®]) 7 days before the study.
 - d. Any medications (eg, corticosteroids, certain antidepressants [eg, citalopram, fluoxetine], nutritional/homeopathic supplements [eg, fish oil, Vitamin E, omega 3, ginko biloba, ginger, St John's Wart, green tea, ginseng, feverfew, saw palmetto, turmeric, bromelain]) or foods (eg, pineapple) that have, or have been reported to have anticoagulant effects within 14 days of treatment.
 - e. Antibiotics, such as penicillin and cephalosporin within 48 hours of treatment.
- 5. Used any of the following for the treatment of cellulite on a buttock within the timelines identified below or intends to use any of the following at any time during the study:
 - a. Liposuction in a buttock during the 12-month period before injection of QWO (CCH-aaes).
 - b. Injections (eg, mesotherapy, dermal fillers, biostimulatory fillers); radiofrequency device treatments; laser treatment; buttock implant treatment; cryolipolysis; or surgery (including subcision and/or powered subcision) within a buttock during the 12-month period before QWO (CCH-aaes) injection.
 - c. Any investigational treatment for cellulite on a buttock during the 12-month period before injection of QWO (CCH-aaes).
 - d. Endermologie[™] or similar treatments in a buttock during the 6-month period before injection of QWO (CCH-aaes).
 - e. Massage therapy for cellulite within a buttock during the 3-month period before injection of QWO (CCH-aaes).
 - f. Creams (eg, Celluvera[™], TriLastin[®]) and/or home therapies to prevent or mitigate cellulite within a buttock during the 2-week period before QWO (CCH-aaes) injection.
- 6. Is presently nursing or providing breast milk or intends to do so during the study.
- 7. Intends to become pregnant during the study.
- 8. Intends to initiate an intensive sport program regimen, exercise program regimen, or intensive weight reduction program during the study.
- 9. Has recently tanned or intends to use any tanning spray or tanning booths during the study.

- 10. Intends to engage in strenuous activity within 48 hours after the first injection of QWO (CCH-aaes).
- 11. Has received an investigational drug or treatment within 30 days prior to injection of QWO (CCH-aaes).
- 12. Has a known systemic allergy to collagenase or any other excipient of QWO (CCH-aaes).
- 13. Has a known systemic allergy or local sensitivity to any of the mitigation treatments or included excipients (ie, arnica patches, INhance Post-injection Serum).
- 14. Has received any collagenase treatments at any time prior to treatment in this study.
- 15. Was a subject in a previous cellulite clinical study of CCH (EN3835, QWO [CCH-aaes]).
- 16. For subjects allocated to PDL treatment

Subjects will be excluded from PDL treatment if they have any contraindications to PDL as indicated in the manufacturer's documentation, for example but not limited to:

- a. previous exposure to photosensitizing medications, food and/or supplements or other photosensitizing agents within 2 weeks of QWO (CCH-aaes) treatment
- b. exposure to Accutane[®] (isotretinoin) within 6 months of QWO (CCH-aaes) treatment.

5.3. Lifestyle Considerations

Subjects will be instructed to refrain from strenuous exercise for 48 hours after the first treatment with QWO (CCH-aaes).

Subjects should avoid medications, homeopathic supplements, or foods as advised by the physician prior to QWO (CCH-aaes) treatment.

Subjects should not use any tanning spray or tanning booths during the study.

5.4. Screen Failures

Screen failures are defined as subjects who consent to participate in this study but do not subsequently receive an injection of QWO (CCH-aaes). Screening procedures will be conducted on Day -14, prior to receiving QWO (CCH-aaes) injection. If mitigation treatments could not be procured within the 14-day Screening Period, subjects can be rescreened after the Screening Period.

Subjects who do not meet all of the eligibility criteria will be deemed a screen failure and the following information must be recorded for all subjects who are screen failures:

- Demography (age, gender, race/ethnicity).
- Reason for screen failure.
- Which eligibility criterion was not met.
- Any AEs (including serious adverse events [SAEs]) experienced by the subject.

6. STUDY TREATMENT

Study treatment comprises QWO (CCH-aaes) and mitigation treatments.

6.1. Selection and Marking of Dimples

To ensure that the contralateral buttock that does not receive mitigation treatment can serve as its own control, and that a similar level of injection site bruising will be induced, subjects should have a similar number of dimples requiring treatment. Subjects can be treated with up to 12 injections of QWO (CCH-aaes) on each buttock. The number of injections of QWO (CCH-aaes) administered to the right and left buttocks should be identical on Day 1. The number of injections may differ between treatment sessions, eg, 12 injections in each buttock in the first treatment session followed by fewer injections per buttock at the second and third treatment sessions as dimples improve.

For treatment, the investigator or qualified designee will select up to 12 dimples within each treatment area (each buttock) that are well-defined, evident when the subject is standing, and suitable for treatment.

For each dimple selected for treatment, the investigator or qualified designee will choose injection sites (injection sites within a dimple should be spaced approximately 2 cm apart, if a dimple requires more than 1 injection; locating at least 1 injection site at the nadir, if present, of the dimple). Each injection site will be marked with a "dot" using a surgical marker. For round dimples, the "dot" will be placed in the center of the dimple; for elongated dimples, "dots" will be spaced out approximately 2 cm along the longer axis of the dimple. The investigator or qualified designee will then use a surgical marker to circle each of the dimples selected for treatment.

6.2. Treatment Administration

6.2.1. QWO (CCH-Aaes)

QWO will be provided by Endo Pharmaceuticals Inc.

Dosage and Mode of Administration: QWO (CCH-aaes), 0.84 mg, injected subcutaneously per buttock with both buttocks treated for a total dose of 1.68 mg. For each buttock, a dose of up to 0.84 mg of QWO (CCH-aaes) in 3.6 mL will be administered as up to 12 subcutaneous injections (0.3-mL injection administered as three 0.1-mL aliquots per injection). There will be 3 treatment visits at intervals of approximately 21 days as described in schedule of assessments.

To induce a similar extent and severity of bruising in each buttock, approximately the same number of injections should be administered to the left and to the right buttock. However, the number of injections per buttock may differ among treatments. The number of injections administered to each buttock on Day 1 must be recorded. The volume and dose of injection at each treatment visit will be injected per the QWO Prescribing Information. QWO will be provided in cartons containing 1 QWO 1.84-mg single-dose vial and 1 diluent for QWO 8-mL single-dose vial.

6.2.2. Mitigation Treatments

Mitigation treatments will be provided locally by each investigator/subject.

At the investigator's discretion and with consent of the subject, mitigation treatments provided after the first treatment session of QWO (CCH-aaes), can be administered after the second and third QWO (CCH-aaes) treatment sessions. Mitigation treatments administered after each treatment session with QWO (CCH-aaes) will be recorded as concomitant medications (Section 6.4).

Cohort 1 will serve as a control and no mitigation treatment will be administered.

Compression Garments (Cohort 2)

Subjects will be instructed to wear a commercially available compression garment (ie, SPANX Grade 3) after the injection on Day 1, for 24 hours per day for 7 days after the injection (Day 1 - 8). Garments may be removed for personal hygiene and when the subject is being evaluated at the investigator's office during study visits. Subjects should be informed that ill-fitting compression garments may contribute to pain.

Instant cold packs (Cohort 3)

Instant cold packs should be applied **to the right buttock only** for 5-10 minutes immediately after the injection of QWO (CCH-aaes) while the subject is lying in prone position.

Arnica Gel Patches (OcuMend) (Cohort 4)

Subjects will be instructed to apply OcuMend gel patches (arnica montana 50% and ledum palustre) immediately after the CCH-aaes injection **to the right buttock only** BID on Days 1 and 2 for a total of 4 doses. One or 2 patches per application may be required depending on the extent of the bruising.

INhance Post-Injection Serum with TriHex Technology® (Cohort 5)

INhance Post-injection Serum will be applied by investigators at the site of injections on Day 1 **on the right buttock only** and then by the subject or subject's associate QID for up to 7 days after injection or until resolution of bruising according to the product instructions. The serum is available in a small 10-mL tube with a chilled tip. A small amount of the serum will be applied on the skin and around the injection site and gently rubbed in using the cooling applicator.

Pulse Dye Laser Treatment (Cohort 6)

Investigators will apply laser treatment with PDL to the bruising observed **on the right buttock only** as a single treatment between Days 1 (same day of QWO [CCH-aaes) injection) and Day 7 after QWO (CCH-aaes) treatment.

The investigator can adjust laser settings at his/her discretion. Laser settings will be recorded in detail to allow comparability across sites. Only select sites will be administering laser treatment.

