The main target chromophore of PDL (585/595 nm) is oxyhemoglobin (absorption peak: 577 nm), which results in its effectiveness in hastening the resolution of ecchymoses. Among its other uses, PDL has been used to treat vascular lesions and post-operative ecchymoses after facial cosmetic procedures (Mayo et al, 2013; Verner et al, 2019).

Defatta et al (2009), used PDL to treat 20 patients with ecchymosis due to facial cosmetic surgeries (ie, cervicofacial rhytidectomy, facial lipocontouring). On post-operative Day 5, half of the bruise was treated. A 10-mm spot size was used, with pulse duration of 6 ms, fluence of 6 J/cm², and cryogen spray for 30 ms with a 20-ms delay for 3 passes. The patients returned 48-72 hours later for PDL of the untreated areas under the same parameters, and had a final follow-up assessment 48 hours after. Photographs of the treated areas were obtained before and after PDL treatment. Ecchymoses captured on the photographs was graded on a scale of 0 to 3 (with a score of 3 indicating severe ecchymosis) by 3 blinded independent observers. PDL treatment resulted in a 63% mean improvement in ecchymosis scores within 48 to 72 hours. The authors indicated that in their experience, maximal efficacy of PDL was observed when it was performed between 5 and 10 days post-operatively.

Karen et al (2010), used PDL to treat 10 patients with ecchymosis due to cosmetic procedures or traumatic injury. Each subject served as his or her own control: subjects with 2 ecchymoses had 1 treated; those with a single lesion had half treated. Photographs were taken before treatment and at 24 hours, 48 hours, and 7 days after treatment. Treated bruises were between 24 and 72 hours old. Subjects received a single treatment with the 595-nm V-Beam PDA (Candela Corp, Wayland, Massachusetts) with the following settings: spot size, 10 mm; fluence, 7.5 J/cm²; and pulse duration, 6 ms. The Dynamic Cooling Device (Candela Corp) was set at 30 ms with a 20 ms delay. Two (2) blinded assessors graded bruise severity from 0 to 10 (0, no bruise; 10, worst bruising). Forty-eight (48) hours after treatment, the average improvement was 76% and 37% for treated and untreated lesions, respectively. One (1) week after treatment, treated and untreated and untreated bruises had improved by 87% and 81%, respectively.

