5.7. Efficacy Evaluation

Efficacy parameters will be summarized for each mitigation group based on the Evaluable Population, unless otherwise stated. Missing values will not be imputed, and only observed data will be summarized.

For mitigation treatments that are bilaterally administered (e.g. compression garments in cohort 2), efficacy parameters will be compared to the control arm (cohort 1). For mitigation treatments that are unilaterally applied (e.g. instant cold packs, arnica patches, INhance, and PDL treatment in cohorts 3-6, which are applied to the right buttock only), subjects will serve as their own control. In these cases, efficacy parameters from mitigation treatment (right buttock) will be compared to contralateral buttock with no mitigation treatment (left buttock). There will be no formal comparison of efficacy parameters between mitigation treatments.

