5.7.1.2. Mitigation

The following information regarding mitigation treatments will be summarized for the treated buttock(s), by cohort:

• Number of mitigation treatment sessions per subject per QWO treatment cycle

• For subjects who had mitigation treatment done, the type of mitigation treatment received, by treatment visit

Note that for Cohort 2, mitigation treatment was administered to both left and right buttocks. For Cohorts 3-6, mitigation treatment was administered to right buttock only. Cohort 1 did not receive mitigation treatment and therefore will not be included in mitigation treatment summaries.

A subject listing containing mitigation treatment administration information will be provided.

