5.7.2. Primary Endpoint and Secondary Endpoints – Bruising Level

For each cohort, results at each level of bruising on the Investigator Assessment of Bruising Severity Scale (see section 2.7.1) will be summarized by visit and by buttock for each subject using counts and percentages. Results and changes from baseline evaluation rating will also be summarized using descriptive statistics (mean and SD).

A listing of Investigator Assessment of Bruising Severity ratings will be provided.

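### Cohort 6 may be lasered as late as Day 7, but the primary bruising rating is at Day 4 and nothing requires the laser first or separates ratings made before it

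*Protocol*

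**What the plan says.** Cohort 6 receives PDL on the right buttock only, "as a single treatment between Days 1 (same day of QWO [CCH-aaes) injection) and Day 7 after QWO (CCH-aaes) treatment" (Protocol 6.2.2). Footnote o to the schedule of assessments, SAP Table 2 and SAP 2.4.2.5 repeat this window without narrowing it.

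The primary endpoint is the proportion of subjects, by buttock, at each level "on the Investigator Assessment of Bruising Severity Scale, at Day 4, 3 days after QWO (CCH-aaes) injection" (Protocol 3.1). Day 4 is also the first named time point for the investigator and subject improvement scales (I-BIS and S-BIS).

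The nearest statement about order is in Protocol 4.1: "After the first mitigation treatment session, on Days 4 and 7, the effect of mitigation treatments on the severity of bruising will be assessed".

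In the analysis, SAP 5.7 takes the right buttock in Cohorts 3 to 6 as mitigated and compares it with the left. SAP 5.7.2 says severity results "will be summarized by visit and by buttock for each subject using counts and percentages". SAP 3.3.3 keeps subjects in their assigned cohort whatever they received. The Evaluable Population (SAP 4.2) needs a bruising assessment after the first QWO dose, not after mitigation. The exposure summary in SAP 5.7.1.2 gives the number of sessions and "the type of mitigation treatment received, by treatment visit".

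**The concern.** Cohort 6 is the only one of the five mitigation cohorts whose treatment may begin after the primary rating. Compression garments, cold packs, arnica patches and serum all start on Day 1. A Cohort 6 subject not yet lasered at Day 4 appears under the PDL heading with two untreated buttocks, so her right-left difference contains no laser effect. Her I-BIS and S-BIS forms ask for a comparison with a treated buttock that does not yet exist.

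Late treatment is realistic. PDL is aimed at bruising that is already visible, and the laser background in Protocol 2.3 points both ways. One facial surgery series reported that "maximal efficacy of PDL was observed when it was performed between 5 and 10 days post-operatively". In another series, "Treated bruises were between 24 and 72 hours old". A site guided by the first would laser on Day 5 or later without any deviation.

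A reader of the tables would not see this. Table 14.2.2 groups mitigation by QWO session and does not show the day of laser. These counts and percentages are the study's main evidence on mitigation, so a Day 4 summary that mixes lasered and unlasered buttocks understates whatever PDL does.

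**Working it through.** **Inputs.** Cohort size 8 (Protocol 9.1; the plan's total is reproduced by 6 × 8 = 48). Laser window Days 1 to 7 (Protocol 6.2.2). Primary rating at Day 4 (Protocol 3.1). Scheduled visits inside the window on Days 1, 2, 4 and 7 (schedule of assessments). No alpha, power or effect size is stated, so no power calculation applies. The distribution of laser days is not in the documents, so the three patterns below are assumptions.

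**Formulas.** Let p be the probability that a subject's rating precedes her laser, and k the number of such subjects among 8.

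- Expected k = 8p.
- If the laser effect is the same in every lasered subject and zero before laser, the mean right-left difference keeps (8 − k)/8 of its size.
- Chance of at least one such subject = 1 − (1 − p)^8, taking subjects as independent.

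Each range runs from same-day laser given before the rating to same-day laser given after it.

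**Bounds the plan permits.** k = 0 keeps 100% of the contrast; k = 8 keeps none.

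**Illustrations at Day 4.**

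| Laser days, used equally | p | Expected k of 8 | Contrast kept |
|---|---|---|---|
| (a) Visits on Days 1, 2, 4, 7 | 1/4 to 2/4 | 2 to 4 | 75% to 50% |
| (b) Days 2, 3, 4 (bruise age about 24 to 72 hours) | 0 to 1/3 | 0 to 2.7 | 100% to 67% |
| (c) Any of Days 1 to 7 | 3/7 to 4/7 | 3.4 to 4.6 | 57% to 43% |

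**Chance that at least one Day 4 rating precedes laser.** Pattern (a), lower end: 1 − 0.75^8 = 0.90. Pattern (c), upper end: 1 − (3/7)^8 = 0.999.

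**Other visits.**

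- Day 2, pattern (a): p = 2/4 to 3/4, so 4 to 6 of 8 ratings precede laser.
- Day 7, pattern (a): p = 0 to 1/4, so 0 to 2 of 8.
- Day 7, pattern (b): none.
- Day 7, pattern (c): p = 0 to 1/7, so 0 to 1.1 of 8.
- Days 14 and 22: none, because the window has closed.

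The retention figures are approximate. A rating made a few hours after laser need not show the full effect, and the primary endpoint is a five-level distribution rather than a mean.

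**The case against.** The strongest reply is that the intended order is already written down: Protocol 4.1 places the Day 4 and Day 7 assessments after the first mitigation session. That shows intent, but it sets no deadline for the laser and no order for a laser given on a visit day. It sits beside an explicit Day 1 to Day 7 window in four places.

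Second, Day 7 is a named secondary time point for I-BIS and S-BIS, severity is tabulated there too, and few ratings at that visit would precede laser. This stands: a planned first-week readout is largely intact. It does not repair the primary time point.

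Third, Protocol 6.4 has study treatment given at the site, so laser on Days 3, 5 or 6 would need an extra attendance. This also stands, and it makes pattern (a) a better guide than pattern (c).

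Fourth, the data permit a repair afterwards. Mitigation dates are recorded (SAP 3.3.2) and listed (Listing 16.2.5.2), records removed from an analysis must be footnoted (SAP 6.5.1), and the I-BIS listing has a field for why an assessment was not done. None of these is a rule for this case. The listings show dates rather than times for mitigation and for ratings, so they cannot settle same-day order. Whether the eCRF or operations manual captures it cannot be seen from these documents. The study schema figure (Protocol 1.2) was also not available to check.

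Finally, subjects lasered before Day 4 are a subset chosen by the investigator, perhaps by bruise severity. This is a real limit on any before/after split, and it is why the all-subject row must stay.

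**Conclusion.** The concern holds and should be fixed. Under the plan as written, a fully compliant Cohort 6 subject can enter the primary Day 4 summary as laser-treated before any laser has been given, and no planned analysis identifies her.

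The size depends on when sites choose to laser. The only bound the documents support is 0 to 8 of 8. Laser at scheduled visits in equal numbers is the most natural of the three illustrations, and it would halve the expected contrast at worst and remove a quarter of it at best. That rests on equal use of visits and a uniform laser effect. The reach is limited to one of six cohorts in an open-label descriptive study, so no error rate is at stake. Later ratings compensate only in part, because bruising generally resolves within 21 days.

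**What to change.** The simplest change is one protocol sentence: in Cohort 6, PDL is given before the Day 4 rating. The cost is the loss of late laser treatment, which the sponsor may want to study given its own background section.

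If the Day 1 to Day 7 window is kept:

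- Derive a before/after-PDL flag for each Cohort 6 rating from the mitigation date already recorded, and add an eCRF tick for order when both fall on the same day.
- Show the Cohort 6 severity, I-BIS and S-BIS results at Days 2, 4 and 7 in three rows with n: all subjects by assigned cohort (as now planned), after PDL, and before PDL.
- Read the laser effect from the after-PDL row, with a footnote that timing was the investigator's choice and n may be small (4 to 6 at Day 4 under pattern (a)).
- Add a row with the study day of PDL to Table 14.2.2.

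This costs one derived variable, one eCRF field and some table rows. No planned output is lost, and the sample size does not change.
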